CLINICAL PROTOCOL

Human Umbilical Cord Mesenchymal Stem Cells to Treat Decompensated Liver Cirrhosis

Objective: To evaluate the safety and efficacy of human umbilical cord mesenchymal stem cells in the treatment of decompensated liver cirrhosis

Clinical research sponsor: The Treatment and Research Center for Infectious Diseases, Beijing 302 Hospital of PLA

Principal Investigator: [name]

Unit responsible for clinical research: The Treatment and Research Center for Infectious Diseases, Beijing 302 Hospital of PLA

Protocol Version Number: V 2.0

Registration Number: NCT01220492

Revision date: October 12, 2010

Title	Human Umbilical Cord Mesenchymal Stem Cells to Treat Decompensated Liver Cirrhosis
Registration Number	NCT01220492
Indication	Decompensated liver cirrhosis associated with chronic hepatitis B
Objectives	Primary objective: To evaluate the efficacy of human umbilical cord mesenchymal stem cells to treat decompensated liver cirrhosis. Secondary objective: To evaluate the safety of human umbilical cord mesenchymal stem cells in the treatment of decompensated liver cirrhosis.
Unit responsible for clinical research	Beijing 302 Hospital of PLA
Clinical Trial Type	Initiated by researchers
Participants	Patients with decompensated liver cirrhosis associated with Chronic Hepatitis B
Sample Size	250 cases
Study Design	Prospective, single center, open label, randomized controlled trial
Investigational Agents	Umbilical cord mesenchymal stem cells (UC-MSC) derived from healthy fetal umbilical cords and processed by pulverization, centrifugation, culture, and activation in vitro .
Administration Regimen	Treatment group: Conventional treatment + UC-MSC treatment, 0.5×10^6 cells/kg body weight, infused intravenously three times at 4-week intervals. Control group: Conventional treatment according to Chronic Hepatitis B Prevention and Treatment Guidelines (APASL 2008), Cirrhotic Ascites Prevention and Treatment Guidelines (AASLD 2004), and Cirrhotic Variceal Hemorrhage Prevention and Treatment Guidelines (AASLD 2008).
Inclusion Criteria	 Patients aged 18 to 65 years. Patients testing positive for serum hepatitis B surface antigen (HBsAg) for more than 6 months. Diagnosis of decompensated liver cirrhosis, which was defined as liver cirrhosis with serious complications, such as ascites, hepatic encephalopathy, and esophageal and gastric variceal hemorrhage according to the Prevention and Treatment of Chronic Hepatitis B (China 2009). Negative pregnancy test (female patients of fertile age). Willing to participate in this clinical trial, and able to understand and

SYNOPSIS

	provide informed consent.
Exclusion Criteria	 (1) Hepatocellular carcinoma or other malignancies. (2) Pregnancy or lactation. (3) Sepsis. (4) Presence of significant extrahepatic biliary disease (e.g., common bile duct (CBD) stone and primary sclerosing cholangitis (PSC)). (5) Severe renal, cardiac, or respiratory disease. (6) Active thrombosis of the portal or hepatic veins.
Withdrawal criteria	 The participant's request to stop test for lack of efficacy, intolerance, or adverse reactions. The participant's compliance was poor, and they could not infuse stem cells as required or follow the protocol. The female participants were pregnant or lactating during the clinical trial. Any clinical adverse event (AE), laboratory abnormality or intercurrent illness which, in the opinion of the investigator, indicates that continued participation in the study is not in the best interest for the subject. Other conditions unsuitable to continue test in the opinion of the investigator.
Termination Criteria	 Serious safety problems occurred during the test. Termination requested by clinical research sponsor (such as funding or management reasons). Termination requested by independent ethics committee or administrative department.
Visit Schedule	Treatment times: Week 0, week 4, week 8. Follow-up periods: Week 2, week 4, week 8, week 12, week 24, week 48, month 24, month 48, month 60, month 75.
Endpoints	 Primary endpoints (1) Overall survival rate during 75 months posttreatment follow up. (2) Hepatocellular carcinoma (HCC)-free survival rate during 75 months posttreatment follow up. Secondary endpoints (1) Liver function including the levels of albumin (ALB), prothrombin activity (PTA), total bilirubin (TBIL), and cholinesterase (CHE). (2) Complications including gastrointestinal hemorrhage, abdominal infection, hepatic encephalopathy, and hepatorenal syndrome during 48 weeks after the first UC-MSC infusion.

VISIT SCHEDULE

	Screening	On treatment & Posttreatment visit period										
Visit item	period	Treatment 1	Visit 1	Treatment 2	Treatment 3	Visit 2	Visit 3	Visit 4	Visit 5	Visit 6	Visit 7	Visit 8
Visit time	-7~0 Day	Week 0	Week 2 ±2 days	Week 4 ±2 days	Week 8 ±7 days	Week 12 ±7 days	Week 24 ±14 days	Week 48 ±14 days	Month 24 ±15 days	Month 48 ±15 days	Month 60 ±30 days	Month 75 ±30 days
Informed consent	×											
Demographics	×											
Medical history	×											
Weight	×	×	×	×	×	×	×	×				
Vital signs	×	×	×	×	×	×	×	×				
Physical examination	×	×	×	×	×	×	×	×				
Urine pregnancy test (female)	×		×		×	×	×					
Routine blood test	×		×	×	×	×	×	×				
Routine urine test	×		×	×	×	×	×	×				
Biochemical test	×		×	×	×	×	×	×				
Coagulation function	×		×	×	×	×	×	×				

	Samooning	On treatment & Posttreatment visit period										
Visit item	period	Treatment 1	Visit 1	Treatment 2	Treatment 3	Visit 2	Visit 3	Visit 4	Visit 5	Visit 6	Visit 7	Visit 8
Visit time	-7~0 Day	Week 0	Week 2 ±2 days	Week 4 ±2 days	Week 8 ±7 days	Week 12 ±7 days	Week 24 ±14 days	Week 48 ±14 days	Month 24 ±15 days	Month 48 ±15 days	Month 60 ±30 days	Month 75 ±30 days
HbA1c	×											
Five items of hepatitis B	×											
HBV DNA	×					×	×	×				
AFP	×					×	×	×				
Anti-HCV	×											
Anti-HIV	×											
Abdominal ultrasound	×					×	×	×				
Chest X-ray	×											
Electrocardiogra m (ECG)	×											
Adverse events (AEs)			×	×	×	×	×	×				
Complications			×	×	×	×	×	×				
UC-MSC infusion		×		×	×							

Visit item	Samoning	On treatment & Posttreatment visit period										
	period	Treatment 1	Visit 1	Treatment 2	Treatment 3	Visit 2	Visit 3	Visit 4	Visit 5	Visit 6	Visit 7	Visit 8
Visit time	7 0 Dov	Wook 0	Week 2	Week 4	Week 8	Week 12	Week 24	Week 48	Month 24	Month 48	Month 60	Month 75
visit time	-/~0 Day	WEEK U	±2 days	±2 days	±7 days	±7 days	±14 days	±14 days	±15 days	±15 days	±30 days	±30 days
Survival status												
(follow-up by									×	×	×	×
telephone)												
Occurrence of												
HCC									~	~	~	~
(follow-up by									X	X	X	X
telephone)												

Abbreviation

ACLF	acute-on-chronic liver failure
ADL	activities of daily living
AE	adverse events
AFP	alpha-fetoprotein
ALB	albumin
ALT	alanine aminotransferase
AST	aspartate aminotransferase
СНЕ	cholinesterase
CLcr	creatinine clearance rate
Cr	creatinine
CRF	case report form
ECM	extracellular matrix
FAS	full analysis set
FDA	Food and Drug Administration
GCP	Good Clinical Practice
GMP	Good Manufacturing Practice
Hb	hemoglobin
HbA1c	glycosylated hemoglobin
HBsAg	hepatitis B surface antigen
HBV	hepatitis B virus
НСС	hepatocellular carcinoma
HCV	hepatitis C virus
HGF	hepatocyte growth factor
HIV	human immunodeficiency virus

HSC	hepatic stellate cells
IL	interleukin
INR	international standardization ratio
MedDRA	Medical Dictionary for Regulatory Activities
MELD	model of end-stage liver disease
MSC	mesenchymal stem cells
NK	natural killer cells
NYHA	New York Heart Association
PLT	platelet
PPS	per protocol set
РТ	prothrombin time
РТА	prothrombin activity
SAE	serious adverse event
SS	safety set
TBIL	total bilirubin
TEAE	treatment emergent adverse event
TGF	transforming growth factor
TNF	tumor necrosis factor
Treg	regulatory T cell
UC-MSC	umbilical cord mesenchymal stem cells
ULN	upper limit of normal
WBC	white blood cells

CATALOGUE

1Background	1
2 Objectives	2
3 Study Design	2
3.1 Overall design and sample size	2

13.7 Data storage	
14 Risks and benefits	
15 Papers published	36
16 Ethics	
17 References	

1 Background

Liver cirrhosis is one of the late stages of progressive hepatic fibrosis, which is characterized by the formation and accumulation of an extracellular matrix, and leads to the progressive distortion of the hepatic architecture ^[1]. In China, the most important cause of liver cirrhosis is chronic hepatitis B virus (HBV) infection. Liver cirrhosis usually progresses irreversibly into the advanced stage, for example, the decompensated stage, which is characterized by a series of clinical manifestations, including ascites, variceal hemorrhage, and hepatic encephalopathy, with high mortality. Liver transplantation is the only treatment that can improve the survival of patients with decompensated liver cirrhosis; however, this procedure is associated with several limitations, such as the severe shortage of donor livers, long waiting lists, multiple complications, and high cost. Therefore, there is an urgent need to find an alternative therapeutic approach to treat decompensated liver cirrhosis that is both safe and effective.

Stem cells, including embryonic stem cells and adult stem cells, have strong practicality and favorable clinical prospects. Mesenchymal stem cells (MSC), a kind of adult stem cell, are multipotent stem cells derived from mesenchymal cells, which have unlimited self-renewal ability and the potential to differentiate into specific cell lineages, including hepatocytes. MSC have been reported to be successfully isolated from different tissues with the common characteristics, including bone marrow ^[2], umbilical cord blood ^[3], adipose tissue ^[4], and the placenta ^[5]. Umbilical cord tissue is an especially promising source of MSC. All umbilical veins, umbilical arteries, sub-amniotic tissues, Wharton's jelly, and umbilical cord perivascular tissues could be sources of MSC. Three criteria have been defined by the International Society for the isolation and purification of MSC for cellular therapy: 1) Adherence to plastic under standard culture conditions; 2) expression of CD105, CD73, and CD90; 3) lack of expression of hematopoietic and endothelial markers including CD11b, CD14, CD31, CD34, CD45, and HLA-DR; differentiation into adipocytes, osteocytes, and chondrocytes *in vitro* under specific culture conditions [^{6]}. In the past decade, MSC therapies have emerged as a novel alternative to treat end-stage liver diseases.

The potential for stem cells to differentiate into hepatocytes cells was confirmed recently. In particular, bone marrow derived mesenchymal stem cells (BM-MSC) transplantation has been applied in the clinic to treat several human diseases such as graft-versus-host disease (GVHD), cardiac injury and brain injury, displaying good tolerance and efficiency ^[7]. BM-MSC have also been used to treat human liver diseases, such as liver failure and liver cirrhosis. In a phase 1 study, autologous BM-MSC transplantation showed potential to decrease the MELD score and increase serum albumin in patients with decompensated liver cirrhosis ^[8, 9].

MSC can exert anti-fibrotic effects directly or indirectly by inhibiting the proliferation of hepatic stellate cells (HSC), extracellular matrix (ECM) deposition and inducing HSC apoptosis. HSC, the leading mediators of liver fibrosis, deposit the ECM under conditions of liver injury, pathological factors and cytokines, eventually leading to cirrhosis. Soluble mediators secreted from MSC suppress the proliferation and activation of various immune cells, which reduces the stimulation of pro-fibrosis factors secretion and alleviates fibrosis indirectly. MSC can secrete tumor necrosis factor alpha (TNF-a), interleukin (IL-10), transforming growth factor beta 3 (TGF-β3), and hepatocyte growth factor (HGF) to inhibit the proliferation of HSC and reduce ECM synthesis ^[10, 11]. Moreover, MSC-derived HGF can also accelerate the rate of HSC apoptosis. Hepatocytes differentiated from MSC will also contribute to improving liver function and histopathological grade. However, limited by the difficulty of locating the process, the transformation function requires further study.

To date, several clinical trials of MSC have been registered with ClinicalTrials.gov. The trials aim to evaluate the safety and efficacy of MSC to treat liver disease, such as liver cirrhosis and hepatic failure. Although trials with large patient cohorts and random controlled trials are not yet completed, the current data provide sufficient evidence for the potential of MSC to treat or ameliorate hepatic diseases.

The purpose of this study is to determine whether and how umbilical cord-derived MSC (UC-MSC) can improve the longer term survival of patients with liver cirrhosis. This study will also examine at how well UC-MSC are tolerated and their safety in patients with liver cirrhosis.

2 Objectives

Primary objective: To evaluate the efficacy of human UC-MSC to treat decompensated liver cirrhosis.

Secondary objective: To evaluate the safety of human UC-MSC in the treatment of decompensated liver cirrhosis

3 Study Design

3.1 Overall design and sample size

Overall design: This study follows the principle of Good Clinical Practice (GCP) to carry out a single center, open label, randomized controlled trial.

Participants: The participants are patients with decompensated liver cirrhosis associated with Chronic Hepatitis B (CHB). The total number of patients in this study is 250. After enrollment, the subjects are randomly assigned into the treatment group or the control group at a 1:1 ratio.

The administration regimens are as follows:

Treatment group: Conventional treatment + UC-MSC treatment, 0.5×10^6 UC-MSC/kg body weight, infused intravenously three times at 4-week intervals.

Control group: Conventional treatment according to the Chronic Hepatitis B Prevention and Treatment Guidelines (APASL 2008), the Cirrhotic Ascites Prevention and Treatment Guidelines (AASLD 2004), and the Cirrhotic Variceal Hemorrhage Prevention and Treatment Guidelines (AASLD 2008).

3.2 Endpoints

3.2.1 Primary endpoints

(1) Survival rate during 75 months posttreatment follow up.

(2) Hepatocellular carcinoma (HCC)-free survival rate during 75 months of posttreatment follow up.

3.2.2 Secondary endpoints

(1) Liver function, including the levels of albumin (ALB), prothrombin activity (PTA), total bilirubin (TBIL), and cholinesterase (CHE) during 48 weeks after the first UC-MSC infusion..

(2) Complications, including abdominal infection, gastrointestinal hemorrhage, hepatic encephalopathy, and hepatorenal syndrome during 48 weeks after the first UC-MSC infusion.

3.3 Randomization

Patients will be randomly allocated to the conventional treatment (control) or UC-MSC treatment (UC-MSC infusion) groups at a 1:1 ratio according to a computer-generated randomization list. The randomization list will be generated by third party statistical staff. The randomization code will be assigned to a participant at his or her first visit. The participants will be assigned to the treatment groups corresponding to the randomization code. This is an open-label study; both participants and the study team will be aware of the treatment allocation.

4 Participants

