4.2 Exclusion Criteria

Subjects who meet one of the following conditions will not be allowed to enter the test:

(1) Hepatocellular carcinoma or other malignancies.

(2) Pregnancy or lactation.

(3) Sepsis.

(4) History of HCV infection.

(5) History of HIV infection.

(6) Other liver diseases, including, but not limited to, alcoholic liver disease, non-alcoholic fatty liver disease, drug-induced hepatitis, autoimmune hepatitis, Wilson disease, and hemochromatosis.

(7) ALT or AST \geq 10*ULN.

(8) Creatinine clearance (CLcr) < 50 mL/min (calculated according to the Cockcroft-Gault formula) (Appendix 2).

(9) Diabetes mellitus (HbA1c > 8.5%).

(10) History or family history of mental or neural diseases, especially depression, depressive tendencies, epilepsy, and hysteria.

(11) Severe cardiovascular disease including, but not limited to, uncontrolled hypertension (systolic blood pressure \geq 160 mmHg or diastolic blood pressure \geq 100 mmHg), New York Heart Association (NYHA) cardiac function grade III (Appendix 1) and above, unstable angina pectoris, myocardial infarction, or intracoronary angioplasty occurring within 6 months, QTc interval (QTcF or QTcB) \geq 500 ms, II° or III° atrioventricular block, or other uncontrolled arrhythmias.

(12) Serious diseases of the blood system, including, but not limited to, various anemias and hemophilia.

(13) Serious digestive diseases including, but not limited to, gastrointestinal ulcers and colitis.

(14) Severe respiratory diseases including, but not limited to, pneumonia, pulmonary tuberculosis, chronic obstructive pulmonary disease, and interstitial pulmonary disease.

(15) Allergic constitution or history of severe allergies, especially allergies to stem cell products or ingredients.

(16) History of alcohol or drug abuse within 6 months.

(17) Participation in other clinical trials within 3 months.

(18) Unable or unwilling to provide informed consent or unable to comply with test requirements

(19) Other situations unsuitable to participation in the opinion of the researcher.

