6.2 Screening period: (-7~0 days)

(1) Signing of the informed consent form

The investigator or subinvestigator will fully explain the nature of the study to a subject using the institutional review board (IRB)-approved informed consent document. If the subject agrees to participate in the study, the subject must voluntarily sign an informed consent form before the initiation of any study procedures. A copy of the signed and dated informed consent document will be given to the subject. The signed and dated original consent form will be retained by the investigator. Informed consent must be obtained from all subjects. A subject cannot be entered into the study until he or she has signed and dated on the consent form. The investigator or subinvestigator is responsible for ensuring that the subject understands the risks and benefits of participating in the study and should answer any questions the subject may have during the discussion of informed consent performed before study initiation, as well as during the study period. The investigator or subinvestigator is also responsible for sharing any new information in a timely manner that might affect the subject's willingness to continue his or her participation in the study.

(2) Ask for demographic information and past medical history

The following baseline subject characteristics will be obtained and entered in the CRF: Date of written informed consent by the subject, date of birth, sex, ethnicity, race, inpatient or outpatient status, smoking habit, drinking habit, prior therapy, and medical history. Medical history will include any previous medical condition requiring hospitalization, all concurrent medical conditions, surgical history (within 12 months), time of influenza vaccination (within 12 months), diagnosis of influenza virus infection, and time of onset.

(3) Weight measurement

Weight measurement will be performed before treatment and during each visit, in accordance with the requirements of the study process. The weight test will be performed by the researchers.

(4) Physical examination and vital signs

Physical examination (see table 5) and vital signs (see tables 5 and 6) will be performed before treatment and during each visit, in accordance with the requirements of the study process. The

physical examination is completed by the researcher and judged by the researcher. Blood sample collection and processing will be performed in accordance with standard operating procedures (Appendix 3)

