6.3 Treatment 1 (week 0) baseline phase

- (I) The verification of inclusion criteria and exclusion criteria should be carried out again;
- (2) Weight measurement;
- (3) Vital signs and physical examination;
- (4) Treatment with UC-MSC.

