6.4 Visit 1 (2nd week ±2 days)

- (1) Weight measurement;
- (2) Vital signs and physical examination;
- (3) Urine pregnancy test for women of childbearing age with abnormal menstruation;
- (4) Routine blood tests;
- (5) Routine urine tests;
- (6) Biochemical indexes: Liver function, renal function, blood glucose, and blood lipid;
- (7) Coagulation function;
- (8) Record AEs;
- (9) Complications.

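### Open-label allocation is tied to an undefined first visit with no eligibility sign-off required before it; separately, the synopsis and section 4 eligibility lists disagree

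*Protocol*

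**What the plan says.** **Timing of allocation (Protocol).**

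- Section 3.3: "The randomization code will be assigned to a participant at his or her first visit". The same section says that "both participants and the study team will be aware of the treatment allocation".
- Section 3.1: "After enrollment, the subjects are randomly assigned into the treatment group or the control group at a 1:1 ratio". Enrolment is not defined.
- Section 6.2 places screening at day -7 to 0. Consent, HbA1c, AFP, anti-HCV, anti-HIV, ultrasound and ECG are all done there.
- Section 6.3 (Week 0) opens with "The verification of inclusion criteria and exclusion criteria should be carried out again" and ends with the infusion. It does not mention randomisation, and the visit schedule has no row for it.
- Section 6.4 gives the label Visit 1 to Week 2.
- Section 4.2, item 19 excludes for "Other situations unsuitable to participation in the opinion of the researcher".
- Section 10.2 foresees enrolled patients who then fail screening.
- Section 12.2 makes at least one UC-MSC infusion a condition of the full analysis set. Section 12.3.4 limits the primary analysis to eligible participants who were treated as assigned and followed up.

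**Eligibility lists (Protocol).** The synopsis has 5 inclusion and 6 exclusion criteria; sections 4.1 and 4.2 have 6 and 19. One synopsis exclusion is "Active thrombosis of the portal or hepatic veins", which 4.2 does not name.

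**The concern.** In an open-label trial, the main protection against selection after randomisation is that eligibility is settled before the arm is known and that nobody leaves the analysis afterwards. This protocol secures neither. If the code is out before the Week 0 check, an investigator who knows the arm can judge a sicker patient unsuitable for infusion, and the discretionary item 19 gives the grounds. The analysis rules then remove that patient from the primary comparison of survival and HCC-free survival. If such removals relate to prognosis and differ by arm, the hazard ratio is biased and randomisation no longer protects it.

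The list mismatch is a separate matter. Site staff applying the synopsis and staff applying section 4 would admit different patients, and the Week 0 check has no single standard to verify against. That affects who is in the trial, and it is a patient-safety question as well.

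**Working it through.** **1. Which visit is meant in 3.3?**

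| Reading | Consequence |
|---|---|
| Screening visit (day -7 to 0) | The code is out before the 6.3 check, by 0 to 7 days |
| Week 0 | 6.3 lists the check first, but the order of check and code release is not stated |
| The label Visit 1 (Week 2) | Impossible: the first infusion, at Week 0, already needs the allocation |

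Neither feasible reading makes code release conditional on confirmed eligibility.

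**2. What happens to a patient dropped at the check?** Such a patient is ineligible and untreated, so fails the 12.3.4 condition. In the UC-MSC arm the patient also fails the 12.2 infusion condition. Either way the patient is outside the primary analysis.

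**3. Possible size.** The protocol gives no figure for this, so the following is an illustration.

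- From section 12.1: 125 per arm, and 60% on standard treatment, read as event-free at 60 months (the sentence is garbled). That is 40% events, or 125 × 0.40 = 50 per arm.
- Assumed, not in the documents: no true effect, removal from the UC-MSC arm only, *k* patients removed, and a share *q* of them who would have had an event.
- Observed event rate in that arm = (50 − *kq*)/(125 − *k*).

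| *q* | *k* = 6 | *k* = 12 |
|---|---|---|
| 40% (unrelated to prognosis) | (50−2.4)/119 = 40.0% | (50−4.8)/113 = 40.0% |
| 60% | (50−3.6)/119 = 39.0% | (50−7.2)/113 = 37.9% |
| 80% | (50−4.8)/119 = 38.0% | (50−9.6)/113 = 35.8% |
| 100% | (50−6)/119 = 37.0% | (50−12)/113 = 33.6% |

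**4. Effect on type I error, same assumptions.** With fraction *f* removed, the event-free rate among those retained is *s* = (0.60 − *f*(1 − *q*))/(1 − *f*), with 125(1 − *f*) patients left. The probability that a two-sided 0.05 two-proportion test rejects (normal approximation) is:

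| *q* | *f* = 5% | *f* = 10% | *f* = 20% |
|---|---|---|---|
| 40% | 0.050 | 0.050 | 0.050 |
| 60% | 0.053 | 0.064 | 0.119 |
| 80% | 0.063 | 0.108 | 0.342 |

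For example, with *f* = 10% and *q* = 80%, *s* = (0.60 − 0.02)/0.90 = 0.644. The planned analysis is Kaplan–Meier and Cox, so these values show the order of size only.

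**5. The plan's own power figure.** Section 12.1 states power above 80% with 100 per group. A two-proportion test of 0.60 against 0.85 gives 0.981, so the statement holds. Reordering the eligibility check and code release does not alter it.

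**6. Comparing the exclusion lists.**

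- Shared: 4.2 items 1–3 match synopsis items 1–3.
- Elaborated: items 8 (creatinine clearance), 11 (cardiac) and 14 (respiratory) give detail to synopsis item 5.
- Overlapping: item 18 largely mirrors the synopsis consent criterion.
- Only in 4.2: items 4–7, 9, 10, 12, 13, 15–17 and 19, which is 12 items, including HCV, HIV and ALT/AST ≥ 10 × ULN. The total agrees: 3 + 3 + 1 + 12 = 19.
- Named only in the synopsis: portal or hepatic vein thrombosis, and significant extrahepatic biliary disease.
- Inclusion: treatment with anti-HBV therapy is required only in 4.1, item 6.

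**The case against.** The strongest reply is that the timing is inferred. Section 3.3 does not say screening, and if Week 0 is meant, 6.3 does list the check first. The opening lines of 4.1 and 4.2 admit only patients who meet the criteria, and 3.1 randomises after enrolment, so the sections can be read as eligibility, then enrolment, then allocation. This stands to the extent that a reader might infer that the code is certainly issued before the re-check, or that 3.1 contradicts 3.3; the text supports neither as fact. It does not clear the plan, because 10.2 allows enrolment before screening is passed and no sentence makes release depend on sign-off.

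A reader might also infer that screening results are still outstanding at allocation. The protocol gives no turnaround times, and the gap may be zero days. A second check at Week 0 is not a fault in itself.

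The harm runs mainly through 12.2 and 12.3.4: analysing everyone randomised would remove most of it, whenever the code is released. That is correct, and it is why the fix must reach those sections.

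On the lists, a reader might infer that the mismatch causes exclusions after allocation. It does not; it is a separate inconsistency that leaves the check without one standard. Nor is renal function missing from the synopsis: item 5 covers it in kind, without the threshold. Primary sclerosing cholangitis, one of the synopsis's biliary examples, arguably falls under 4.2 item 6. Bile duct stones and vein thrombosis do not clearly fit any 4.2 item.

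**Conclusion.** Two separate defects stand, and both should be corrected.

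1. The point of open allocation is undefined, and confirmed eligibility is not a condition for it. Together with the Week 0 check, the discretionary criterion and the analysis rules, this lets patients leave the primary analysis after their arm is known. The size cannot be derived from the documents. Under the assumptions shown, removing 6 patients shifts one arm by 1.0 to 3.0 percentage points and removing 12 by 2.1 to 6.4, for 60% to 100% events among those removed. The upper ends, 37.0% and 33.6%, require every removed patient to have had an event and should not be read as the expected effect. If removal is unrelated to prognosis, there is no bias. The protocol permits such removals; nothing in it shows that they would occur.

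2. The synopsis and section 4 contradict each other on eligibility: two exclusions are named only in the synopsis, and one inclusion and about 12 exclusions appear only in section 4. This rests on direct comparison and needs no assumption.

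**What to change.** **Allocation.** In 3.3, state that the third-party statistical staff release the code one patient at a time, only after screening results are in and eligibility is signed off, and before the Week 0 treatment. Move the 6.3 check ahead of code release, or state that a later check does not remove a patient from the analysis. Whether a patient found ineligible late is treated remains a clinical decision, separate from the analysis.

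**Analysis.** Amend 12.2 and 12.3.4 so that every randomised patient stays in the primary analysis in the assigned arm.

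**Eligibility.** Reconcile the synopsis with 4.1 and 4.2 into one list, and use it for the sign-off. Which criteria stand is for the sponsor's clinicians.

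**Cost.** Wording changes, with sample size and power unchanged. Two practical points need checking. Section 3.3 says that third-party staff generate the list but not that they hold or release it, so release may be a new task for them. Allocation may also move by up to 7 days, which may need coordination with product preparation, since 5.2.2 requires contaminant testing before infusion and the protocol does not say how cell preparation is timed against allocation.
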